849 actions. This means that the participant was impaired cognitively to the point that he/she  
850 was unable to treat himself/herself, was unable to verbalize his/ her needs, was  
851 incoherent, disoriented, and/or combative, or experienced seizure or loss of  
852 consciousness. These episodes may be associated with sufficient neuroglycopenia to  
853 induce seizure or loss of consciousness. If glucose measurements are not available  
854 during such an event, neurological recovery attributable to the restoration of glucose to

855                   normal is considered sufficient evidence that the event was induced by a low glucose  
856                   concentration.

857                   • evaluation or treatment was obtained at a health care provider facility for an acute event  
858                   involving hypoglycemia, or the participant contacted the site and received guidance  
859                   following the occurrence of an acute event involving hypoglycemia

860                   When a severe hypoglycemia event occurs (as defined above), a Hypoglycemia Form should be  
861                   completed in addition to the Adverse Event Form. Severe hypoglycemia events should be  
862                   considered to be serious adverse events with respect to reporting requirements. When a severe  
863                   hypoglycemia event occurs during use of a study device, it generally will be considered to be  
864                   unrelated to the device (per section 7.2.5) if the device functioned as intended and there does not  
865                   appear to be a flaw in how the device is intended to function.

866                   **7.2.4 Hyperglycemic/Ketotic Events**

867                   Hyperglycemia not associated with an Adverse Device Effect or discontinuation of the study  
868                   device is only reportable as an adverse event when one of the following criteria is met:

869                   • the event involved DKA, as defined by the Diabetes Control and Complications Trial  
870                   (DCCT) and described below

871                   • the event involved hyperosmolar hyperglycemic syndrome (HHS), as defined by the  
872                   American Diabetes Association and described below

873                   • evaluation or treatment was obtained at a health care provider facility for an acute event  

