874                   involving hyperglycemia or ketosis, or the participant contacted the site and received  
875                   guidance on how to manage the hyperglycemia/ketosis

876                   Hyperglycemic events are classified as DKA if the following are present:

877                   • Symptoms such as polyuria, polydipsia, nausea, or vomiting;

878                   • Serum ketones  $>1.5$  mmol/L or large/moderate urine ketones;

879                   • Either arterial blood pH  $<7.30$  or venous pH  $<7.24$  or serum bicarbonate (or CO2)  $<15$ ; and

880                   • Treatment provided in a health care facility

881                   Hyperglycemic events are classified as HHS if the following are present:

882                   • Symptoms such as polyuria, polydipsia, nausea, or vomiting;

883                   • Plasma glucose levels are very elevated (typically  $>600$  mg/dL);

884                   • Plasma effective osmolarity is  $>320$  mOsm/L;

885                   • Absence of significant ketones; and

886                   • Treatment provided in a health care facility

887                   When a hyperglycemia/ketotic event qualifies as an SAE as defined in section 7.2.1 , a  
888                   Hyperglycemia/DKA Form should be completed in addition to the Adverse Event Form. Events  
889                   meeting DKA or HHS criteria should be considered to be serious adverse events with respect to  
890                   reporting requirements. Hyperglycemia events not meeting criteria for DKA or HHS generally

891 will not be considered as serious adverse events unless one of the SAE criteria in section 7.2.1 is  
892 met.

893 When a hyperglycemia/DKA event occurs during use of a study device, it generally will be  
894 considered to be unrelated to the device (per section 7.2.5) if the device functioned as intended  
895 and there does not appear to be a flaw in how the device is intended to function.

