#### 896 **7.2.5 Relationship of Adverse Event to Study Investigational Device**

897 The study investigator will assess the relationship of any adverse event to be related or unrelated  
898 by determining if there is a reasonable possibility that the adverse event may have been caused  
899 by the study device. The Medical Monitor also will make this assessment, which may or may not  
900 agree with that of the study investigator. Reporting requirements will be based on the Medical  
901 Monitor's assessment as the Sponsor's representative.

902 To ensure consistency of adverse event causality assessments, investigators should apply the  
903 following general guideline when determining whether an adverse event is related:

- 904 • **Unrelated:** The AE is clearly not related to a study drug/device and a likely alternative  
905 etiology exists such as an underlying disease, environmental or toxic factors or other  
906 therapy.
- 907 • **Unlikely Related:** The AE does not follow a reasonable temporal sequence during or after  
908 use of study drug/device and a more likely alternative etiology exists such as an  
909 underlying disease, environmental or toxic factors, or other therapy.
- 910 • **Possibly Related:** The AE occurred in a reasonable time during or after use of study  
911 drug/device; but could be related to another factor such as an underlying disease,  
912 environmental or toxic factors, or other therapy; and there is a possible, though weak,  
913 scientific basis for establishing a causal association between the AE and the study  
914 drug/device.
- 915 • **Probably Related:** The AE occurred in a reasonable time during or after use of study  
916 drug/device; is unlikely to be related to another factor such as an underlying disease,  
917 environmental or toxic factors, or other therapy; and there is a plausible, though not  
918 strong, scientific basis for establishing a causal association between the AE and the study  
919 drug/device.
- 920 • **Definitely Related:** The AE occurred in a reasonable time during or after use of study  
921 drug/device; cannot be explained by another factor such as an underlying disease,  
922 environmental or toxic factors, or therapy; and there is a strong scientific basis for  
923 establishing a causal association between the AE and the study drug/device.
- 924 • **Not Assessable:** Causality of an adverse event cannot be judged because information is  

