### 998       **7.4 Timing of Event Reporting**

999       SAEs possibly related to a study device or study participation and UADEs must be reported by  
1000       the investigator to the Coordinating Center within 24 hours of the site becoming aware of the  
1001       event. This can occur via phone or email, or by completion of the online serious adverse event  
1002       form and device issue form if applicable. If the form is not initially completed, it should be  
1003       completed as soon as possible after there is sufficient information to evaluate the event. All other  
1004       reportable ADEs and other reportable AEs should be submitted by completion on the online form  
1005       within 7 days of the site becoming aware of the event.

1006 The Coordinating Center will notify all participating investigators of any adverse event that is  
1007 serious, related, and unexpected. Notification will be made within 10 working days after the  
1008 Coordinating Center becomes aware of the event.

1009 Each principal investigator is responsible for reporting serious study-related adverse events and  
1010 abiding by any other reporting requirements specific to his/her Institutional Review Board or  
1011 Ethics Committee. Where the JCHR IRB is the overseeing IRB, sites must report all serious,  
1012 related adverse events within seven calendar days.

1013 Upon receipt of a qualifying event, the Sponsor will investigate the event to determine if a  
1014 UADE is confirmed, and if indicated, report the results of the investigation to all overseeing  
1015 IRBs, and the FDA within 10 working days of the Sponsor becoming aware of the UADE per  
1016 21CFR 812.46(b) (2). The Sponsor in conjunction with the Medical Monitor must determine if  
1017 the UADE presents an unreasonable risk to participants. If so, the Sponsor must ensure that all  
1018 investigations, or parts of investigations presenting that risk, are terminated as soon as possible  
1019 but no later than 5 working days after the Sponsor makes this determination and no later than 15  
1020 working days after first receipt notice of the UADE. The investigator(s) may then be required to  
1021 provide approval or acknowledgment of receipt of that notification, and must submit to their  
1022 overseeing IRB as required.

1023 The investigators are also required to report, without unjustified delay, all device deficiencies  

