1066     In addition to the suspension of closed-loop mode use due to a UADE as described above,  
1067     closed-loop system use will be suspended if there are three or more cases of severe  
1068     hypoglycemia or three or more cases of hyperglycemia/ketotic events qualifying as SAEs across  
1069     the entire study in participants who have initiated Control-IQ technology use.

1070     Study activities could be similarly suspended if the manufacturer of any constituent study device  
1071     requires stoppage of device use for safety reasons (e.g. product recall). The affected study  
1072     activities may resume if the underlying problem can be corrected by a protocol or system  
1073     modification that will not invalidate the results obtained prior to suspension.

1074

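### Protocol 7.2.3 and 7.2.4 generally presume severe hypoglycaemia and DKA unrelated on a test that 7.2.5 does not contain, which can slow site reporting of events that the stopping rules count

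*Protocol*

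**What the plan says.** Protocol 7.2.3 treats severe hypoglycaemia as an SAE for reporting and then adds a presumption about cause. In three consecutive pieces, it says that when a severe "hypoglycemia event occurs during use of a study device, it generally will be considered to be" "unrelated to the device (per section 7.2.5) if the device functioned as intended and there does not" "appear to be a flaw in how the device is intended to function". Section 7.2.4 does the same for the other direction: "When a hyperglycemia/DKA event occurs during use of a study device, it generally will be" "considered to be unrelated to the device (per section 7.2.5) if the device functioned as intended", with the same second condition. DKA and HHS are also SAEs for reporting.

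Section 7.2.5 asks the investigator and the Medical Monitor each to judge whether there is a reasonable possibility that the device caused the event; the Medical Monitor's view decides the reporting requirements. Its Unrelated category begins "The AE is clearly not related to a study drug/device and a likely alternative" etiology must exist.

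On timing, Protocol 7.4 states that "SAEs possibly related to a study device or study participation and UADEs must be reported by" the investigator within 24 hours of the site learning of them. Other reportable adverse events have 7 days.

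On stopping, Protocol 7.6.2 says that "closed-loop system use will be suspended if there are three or more cases of severe" hypoglycaemia in the study, or three or more hyperglycaemic or ketotic SAEs. Section 7.6.1 sets a participant-level rule on two episodes of DKA, HHS or severe hypoglycaemia. It also makes continuation after a single DKA or severe hypoglycaemia event depend on the Medical Monitor's agreement. Neither section makes the count depend on relatedness. SAP 13 has the Medical Monitor review all severe hypoglycaemia and DKA cases, whatever their relation to the device, as they happen.

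**The concern.** Assessing safety is a stated objective, and Protocol 1.5 describes the closed-loop system as investigational in this population. Whether automated dosing is safe in type 2 diabetes when the system does what it was designed to do is part of the question. A presumption that turns on correct function steers the site's first judgement away from the device in just those cases.

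That first judgement matters because the reporting limit in 7.4 depends on it. If the label moves an event to the slower limit, the people applying the stopping rules, which ignore relatedness, may learn of it later than SAP 13 implies.

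**Working it through.** The plan gives no figure to reproduce here. The check sets the sections side by side and then sizes the delay by hand.

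**1. The two tests for Unrelated.**
- 7.2.3 and 7.2.4: the device worked as designed, and no flaw in that design is apparent. The presumption is hedged by the word generally.
- 7.2.5: reasonable possibility of causation; Unrelated requires both a clear absence of relation and a likely alternative cause.

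Correct device function is not a criterion in any 7.2.5 category, and it establishes neither part of the Unrelated definition. An event that follows automated dosing in reasonable time, but could have another cause, can meet Possibly Related if there is even a weak scientific basis. Section 7.2.5 counts that category as related.

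**2. The adverse device effect definition.** Section 7.2.1 includes events due to use error, intentional misuse, or inadequate instructions. None of these needs a malfunction. An event can therefore be a device effect under 7.2.1 and be presumed unrelated under 7.2.3 or 7.2.4.

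**3. One event followed through 7.4.** Take a severe hypoglycaemia event with the pump working as designed and no apparent design flaw.
- It is an SAE (7.2.3), presumed unrelated to the device.
- If it is judged possibly related to study participation, or is a UADE, the limit is 24 hours.
- If neither applies, it is another reportable event and the limit is 7 days.

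**4. Size of the delay.** Inputs: 24 hours and 7 days (7.4); 6 weeks = 42 days of closed-loop use; about 5 months of study (Protocol Summary); 30 participants (9.3).
- Added delay per event: 7 − 1 = 6 days at most, counted from site awareness.
- Share of one participant's closed-loop period: 6/42 = 14.3%.
- Share of the study calendar, taking 5 months as 150 days (assumed): 6/150 = 4.0%.
- Added closed-loop exposure before a report is due: 6 × 30 = 180 participant-days if all 30 were on closed loop at once (assumed upper bound), or 6 × 10 = 60 with 10 at once (assumed).

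**5. What depends on the label.**
- Dependent: the 7.4 limit; adverse device effect status (7.2.1); expectedness review (7.2.7); notice to all investigators of serious, related, unexpected events, and site reports to the central IRB of serious, related events (both 7.4).
- Not dependent: the counts in 7.6.1 and 7.6.2; numbers and rates of severe hypoglycaemia, DKA, HHS and SAEs (Protocol 9.8, SAP 8).

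**6. Fit with the stopping rules and SAP 13.** The participant-level rule in 7.6.1 is written for the absence of a malfunction, which is also the situation that the presumption covers. The Medical Monitor's agreement to continuation cannot be given before the Monitor knows of the event. A 7-day site limit cannot assure the review timing in SAP 13.

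**The case against.** The best defence is that both texts are hedged. The presumption is general rather than absolute, and its second condition leaves room for harm from the design itself. Section 7.2.5 calls its categories a general guideline, and the reference to it can be read as sending each case through that assessment. Hypoglycaemia is a risk for anyone using insulin (1.4.1.2), so an alternative cause may well exist. This stands against reading the sections as an automatic rule. It does not supply the missing criterion: a site that follows 7.2.3 and one that follows 7.2.5 can reach different labels for the same event.

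Second, the 24-hour limit also covers SAEs possibly related to study participation. Participation includes new pump settings and weekly exercise challenges, so many of these events could stay on the fast limit. That stands, and it confines the delay to events judged unrelated to both device and participation.

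Third, there are safeguards: Medical Monitor review of each DKA and severe hypoglycaemia event, the Monitor's agreement to continuation, SAE review typically within 24 hours, and notice to the Clinical Study Director (7.5, 7.6.1). These are real, but the 24-hour review in 7.5 runs from reporting, and the others depend on the Monitor or Director learning of the event, normally from the site. They do not shorten the site's limit.

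A reader might also infer that the presumption lowers the safety results or weakens the stopping rules. The documents do not support that: the listed event counts and rates, and the stopping counts, ignore relatedness. Nor is a material effect on UADE counts shown, since seizure from hypoglycaemia, DKA and HHS are already named risks in 1.4.1, and a UADE must be previously unidentified in nature, severity or degree of incidence.

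**Conclusion.** The inconsistency is real and should be corrected. Sections 7.2.3 and 7.2.4 cite 7.2.5 for a presumption that 7.2.5 does not contain and that also conflicts with 7.2.1. The practical effect is limited to timing and classification: at most 6 extra days per event before the site must report, with knock-on effects on adverse device effect status and on notification of related SAEs. The delay arises only if the event is judged unrelated to study participation as well as to the device, and only if the site uses its full limit. How often that would happen cannot be derived from the documents.

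It would be too strong to say that these events become unrelated whenever the device works, or that they all drop to 7-day reporting. The wording is hedged, carries a second condition, and leaves the participation route open. The point still merits action because three events in a small study trigger suspension, and SAP 13 commits to prompt review of severe hypoglycaemia and DKA without regard to cause.

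**What to change.** In Protocol 7.4, apply the existing 24-hour site reporting limit to every severe hypoglycaemia, DKA and HHS event regardless of relatedness. This brings reporting into line with 7.6 and SAP 13.

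In 7.2.3 and 7.2.4, reconcile the presumption with 7.2.5 and 7.2.1: state that the 7.2.5 definitions govern, and that correct device function alone does not establish Unrelated. The guidance sentences need not be deleted.

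The cost is a wording amendment and a few more expedited site reports in a planned cohort of about 30. Stopping thresholds, treatment and the statistical analyses stay as they are.

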#### 896 **7.2.5 Relationship of Adverse Event to Study Investigational Device**

897 The study investigator will assess the relationship of any adverse event to be related or unrelated  
898 by determining if there is a reasonable possibility that the adverse event may have been caused  
899 by the study device. The Medical Monitor also will make this assessment, which may or may not  
900 agree with that of the study investigator. Reporting requirements will be based on the Medical  
901 Monitor's assessment as the Sponsor's representative.

902 To ensure consistency of adverse event causality assessments, investigators should apply the  
903 following general guideline when determining whether an adverse event is related:

- 904 • **Unrelated:** The AE is clearly not related to a study drug/device and a likely alternative  
905 etiology exists such as an underlying disease, environmental or toxic factors or other  
906 therapy.
- 907 • **Unlikely Related:** The AE does not follow a reasonable temporal sequence during or after  
908 use of study drug/device and a more likely alternative etiology exists such as an  
909 underlying disease, environmental or toxic factors, or other therapy.
- 910 • **Possibly Related:** The AE occurred in a reasonable time during or after use of study  
911 drug/device; but could be related to another factor such as an underlying disease,  
912 environmental or toxic factors, or other therapy; and there is a possible, though weak,  
913 scientific basis for establishing a causal association between the AE and the study  
914 drug/device.
- 915 • **Probably Related:** The AE occurred in a reasonable time during or after use of study  
916 drug/device; is unlikely to be related to another factor such as an underlying disease,  
917 environmental or toxic factors, or other therapy; and there is a plausible, though not  
918 strong, scientific basis for establishing a causal association between the AE and the study  
919 drug/device.
- 920 • **Definitely Related:** The AE occurred in a reasonable time during or after use of study  
921 drug/device; cannot be explained by another factor such as an underlying disease,  
922 environmental or toxic factors, or therapy; and there is a strong scientific basis for  
923 establishing a causal association between the AE and the study drug/device.
- 924 • **Not Assessable:** Causality of an adverse event cannot be judged because information is  
925 insufficient or contradictory, and which cannot be supplemented or verified.

926 Where these relatedness categories are used, events determined to be Possibly Related,  
927 Probably Related, or Definitely Related will be considered to meet the reasonable possibility  
928 causality standard for relatedness and necessitate reporting as required (see 21 CFR 312.32  
929 for more information about this standard).

930 **7.2.6 Severity (Intensity) of Adverse Events**

931 The severity (intensity) of an adverse event will be rated on a three point scale: (1) mild, (2)  
932 moderate, or (3) severe. A severity assessment is a clinical determination of the intensity of an  
933 event. Thus, a severe adverse event is not necessarily serious. For example, itching for several  
934 days may be rated as severe, but may not be clinically serious.

935 • MILD: Usually transient, requires no special treatment, and does not interfere with the  
936 participant's daily activities.

937 • MODERATE: Usually causes a low level of inconvenience, discomfort or concern to the  
938 participant and may interfere with daily activities, but is usually ameliorated by simple  
939 therapeutic measures and participant is able to continue in study.

940 • SEVERE: Interrupts a participant's usual daily activities, causes severe discomfort, may  
941 cause discontinuation of study device, and generally requires systemic drug therapy or other  
942 treatment.

943 **7.2.7 Expectedness**

944 For a serious adverse event that is considered possibly related to study device, the Medical  
945 Monitor will classify the event as unexpected if the nature, severity, or frequency of the event is  
946 not consistent with the risk information previously described in the approved labelling of the  
947 study system.

948 **7.2.8 Coding of Adverse Events**

949 Adverse events will be coded using the MedDRA dictionary. To facilitate coding, the site will  
950 enter a preliminary MedDRA code which the Medical Monitor may accept or change (the  
951 Medical Monitor's MedDRA coding will be used for all reporting). The Medical Monitor will  
952 review the investigator's assessment of causality and may agree or disagree. Both the  
953 investigator's and Medical Monitor's assessments will be recorded. The Medical Monitor will  
954 have the final say in determining the causality as well as whether an event is classified as a  
955 serious adverse event and/or an unanticipated adverse device effect.

956 **7.2.9 Outcome of Adverse Events**

957 The outcome of each reportable adverse event will be classified by the investigator as follows:

958 • RECOVERED/RESOLVED – The participant recovered from the AE/SAE without sequelae.  
959 Record the AE/SAE stop date.

960 • RECOVERED/RESOLVED WITH SEQUELAE – The event persisted and had stabilized  
961 without change in the event anticipated. Record the AE/SAE stop date.

962 • FATAL – A fatal outcome is defined as the SAE that resulted in death. Only the event that  
963 was the cause of death should be reported as fatal. AEs/SAEs that were ongoing at the time  
964 of death; however, were not the cause of death, will be recorded as “resolved” at the time of  
965 death.

966 • NOT RECOVERED/NOT RESOLVED (ONGOING) – An ongoing AE/SAE is defined as  
967 the event was ongoing with an undetermined outcome.

968       ◆ An ongoing outcome will require follow-up by the site in order to determine the final  
969        outcome of the AE/SAE.

970       ◆ The outcome of an ongoing event at the time of death that was not the cause of death,  
971        will be updated and recorded as “resolved” with the date of death recorded as the stop  
972        date.

973       • UNKNOWN – An unknown outcome is defined as an inability to access the participant or  
974        the participant’s records to determine the outcome (for example, a participant that was lost to  
975        follow-up).

976       If any reported adverse events are ongoing when a participant completes the study (or  
977       withdraws), adverse events classified as UADEs or related SAEs will be followed until they are  
978       either resolved, or have no prospect of improvement or change, even after the participant has  
979       completed all applicable study visits/contacts. For all other adverse events, data collection will  
980       end at the time the participant completes the study. Note: participants should continue to receive  
981       appropriate medical care for an adverse event after their participation in the study ends.

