761 involving a specific site such as unanticipated problems that occur study-wide or at another  
762 participating entity such as a pharmacy or laboratory. These instances must be reported to the  
763 JCHR IRB within seven (7) calendar days of recognition. The Director of the Human Research  
764 Protection Program (HRPP) will report to the appropriate regulatory authorities if the IRB  
765 determines that the event indeed meets the criteria of an Unanticipated Problem requiring  
766 additional reporting to fulfill the reporting obligations of the HRPP.

767 **7.2 Adverse Events**

768 **7.2.1 Definitions**

769 Adverse Event (AE): Any untoward medical occurrence (including laboratory findings)  
770 associated with study procedures, the use of a device, biologic, or drug in humans, including any  
771 comparator used, whether or not the event is considered related (i.e., irrespective of the  
772 relationship between the adverse event and the device(s) under investigation).

773 Serious Adverse Event (SAE): Any untoward medical occurrence that results in any of the  
774 following outcomes:

775 • Death.

776 • A life-threatening adverse event; (a non-life-threatening event which, had it been more  
777 severe, might have become life-threatening, is not necessarily considered a serious adverse  
778 event).  
779 • Inpatient hospitalization or prolongation of existing hospitalization.  
780 • A persistent or significant disability/incapacity or substantial disruption of the ability to  
781 conduct normal life functions (sight threatening).  
782 • A congenital anomaly or birth defect.

783 An important medical event that may not result in death, be life-threatening, or require  
784 hospitalization may be considered serious when, based upon appropriate medical judgment, it  
785 may jeopardize the patient or subject and may require medical and surgical intervention to  
786 prevent one of the outcomes listed in this definition. Note: If either the Sponsor or investigator  
787 believes that the event is serious, the event must be considered serious and evaluated by the  
788 Sponsor for expedited reporting.

789 Unanticipated Adverse Device Effect (UADE): Any serious adverse effect on health or safety or  
790 any life-threatening problem or death caused by, or associated with, a device, if that effect,  
791 problem, or death was not previously identified in nature, severity, or degree of incidence in the  

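### Protocol 7.2.1 and 7.2.8 give opposite SAE classifications when the investigator says serious and the Medical Monitor does not, and nothing says which one feeds the SAE endpoint

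*Protocol*

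**What the plan says.** Protocol 7.2.1 (Definitions) closes the SAE definition with an either-party rule: "Note: If either the Sponsor or investigator" "believes that the event is serious, the event must be considered serious and evaluated by the" sponsor for expedited reporting.

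Protocol 7.2.8 (Coding of Adverse Events) says the Medical Monitor will "have the final say in determining the causality as well as whether an event is classified as a" "serious adverse event and/or an unanticipated adverse device effect". It also says that the investigator's and the Monitor's assessments are both recorded, but that sentence follows the one on causality and does not mention seriousness.

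Protocol 7.2.5, on relatedness, bases reporting requirements on the "Monitor's assessment as the Sponsor's representative", so the Monitor speaks for the sponsor.

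SAEs are a safety endpoint in Protocol 9.4.3. Protocol 9.8 and SAP 8 call for their number and their rate per 100 person-years during closed-loop use. Protocol 7.6.2 says "closed-loop system use will be suspended if there are three or more cases of severe" "hypoglycemia or three or more cases of hyperglycemia/ketotic events qualifying as SAEs across" the study, among participants who have started Control-IQ. None of these sections says whose seriousness classification is counted.

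**The concern.** Assessing safety is the first stated objective, and the study has a single arm and few participants. Under 7.2.1 an investigator's judgement that an event is serious is enough by itself. Under 7.2.8 one sponsor-side person can set that judgement aside. An SAE count built on 7.2.8 can therefore be lower than one built on 7.2.1 from the same events, and it can never be higher. If the documents do not choose between the rules in advance, the choice falls to whoever prepares the tables, after the event is known. The data are also meant to inform the design of a larger study, so the ambiguity would carry forward.

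**Working it through.** The point rests on no stated figure, so there is nothing to reproduce. The check compares the rules, traces what depends on them, and sizes one reclassification.

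**1. The two rules side by side**, taking the Monitor's view as the sponsor's (7.2.5):

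| Investigator | Monitor | Result under 7.2.1 | Result under 7.2.8 |
|---|---|---|---|
| serious | serious | SAE | SAE |
| not serious | serious | SAE | SAE |
| serious | not serious | SAE | not an SAE |
| not serious | not serious | not an SAE | not an SAE |

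They differ in one row only, and there 7.2.8 always gives the lower count. No section places one rule above the other.

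**2. Which events can fall in that row.** Several 7.2.1 criteria are largely factual: death, inpatient hospitalization, disability, congenital anomaly. Protocol 7.2.3 and 7.2.4 deem severe hypoglycemia, DKA and HHS serious for reporting purposes, and each is also a separate safety endpoint. What remains is mainly judgement: whether an event was life-threatening, or was an important medical event.

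**3. Size for the SAE rate.** Inputs: 30 participants starting and at least 24 completing (Protocol 9.3, SAP 3), with 6 weeks = 42 days of closed-loop use.

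- Exposure = N × 42 / 365.25 person-years.
- N = 24: 24 × 42 / 365.25 = 1008 / 365.25 = 2.76 person-years.
- N = 30: 30 × 42 / 365.25 = 1260 / 365.25 = 3.45 person-years.
- Change per event = 100 / exposure: 100 / 2.76 = 36.2 and 100 / 3.45 = 29.0 per 100 person-years.

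The lower exposure gives non-completers no time at all; the higher assumes that all 30 complete. If 30 start and 24 finish, exposure lies between the two.

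**4. The suspension rule in 7.6.2** has two limbs.

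- Severe hypoglycemia: counted as cases meeting the definition, whatever their SAE status. A reclassification changes nothing.
- Hyperglycemia/ketotic events: counted if they qualify as SAEs. Events meeting DKA or HHS criteria are deemed serious by 7.2.4. Others are SAEs only if a 7.2.1 criterion is met, so they alone are open to disagreement.

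For those remaining events the answer depends on what qualifying as an SAE means. Protocol 7.2.4 uses almost the same phrase and ties it to 7.2.1. On that reading the investigator's view suffices and the count stands. If the phrase means the outcome under 7.2.8, then with exactly three qualifying events one downgrade leaves 3 − 1 = 2 and the threshold is not reached.

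**5. Reporting and follow-up.** Under 7.4 the site's 24-hour report runs from the site's own awareness, and under 7.5 the Monitor reviews after the report, so a later downgrade does not touch it. Extended follow-up under 7.2.9 is for UADEs and related SAEs. Relatedness is the Monitor's decision under 7.2.5 and 7.2.8, and no other section contradicts that.

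**The case against.** The best defence is that the sections govern different stages. The 7.2.1 note ends with evaluation for expedited reporting and can be read as an intake rule; 7.2.8 sits under coding and can be read as the rule for final classification. This is workable, but the documents do not state it. The note first requires that the event be treated as serious, without limiting that to reporting, and neither 9.8 nor the SAP says that the tables use the coded result.

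A second defence is that nothing disappears. Protocol 9.8 tabulates all adverse events by period; severe hypoglycemia, DKA and HHS have their own lines; and SAP 13 lets the Monitor or the sponsor request suspension of the study. This stands, as long as the event remains reportable under 7.2.2. The loss is from the SAE count and rate, not from the record.

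Third, any single event moves a rate on about three person-years by this much, and the figure says nothing about how often the two parties would disagree. That is also right. The size describes sensitivity, not expected bias.

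A reader might go further and infer that a downgrade can defeat the suspension rule in general, or put an SAE on the slower 7-day reporting schedule. The documents do not support either. One limb of 7.6.2 ignores SAE status, DKA and HHS are deemed serious, the wording of 7.2.4 favours the 7.2.1 reading of the other limb, and the initial report precedes the Monitor's review.

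**Conclusion.** The contradiction is real and visible in the text. With the investigator at serious and the Monitor at not serious, 7.2.1 and 7.2.8 cannot both be followed, and the SAP does not settle it. The main consequence is for the SAE endpoint, chiefly for judgement-based events: 29 to 36 per 100 person-years for each reclassified event, assuming 24 to 30 participants with a full 42 days each. How often this would happen is unknown, since the documents give no rate of disagreement.

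The effect on 7.6.2 is conditional. It needs a hyperglycemia/ketotic event short of DKA/HHS, a disagreement over its seriousness, and a reading of the rule that follows 7.2.8 and not 7.2.1. The severe hypoglycemia limb and the initial 24-hour report are unaffected.

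**What to change.** 1. Reconcile Protocol 7.2.8 with 7.2.1 so that the Monitor's final say does not take an event the investigator classified as serious out of the SAE tabulation.
2. Record both seriousness assessments, as 7.2.8 already does for causality.
3. State in SAP 8 that an event classified as serious by either party is counted as an SAE.
4. Reconcile 7.6.2 with 7.2.1 and 7.2.8 so that it is clear which classification its hyperglycemia/ketotic limb refers to. This asks only for consistent wording, not for a different suspension rule.

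The cost is a few sentences across the two documents and one more recorded assessment per event. The SAE count may come out slightly less favourable.
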